## Document History – Changes compared to previous final version of SAP

Date	Time point	Reason for update	Outcome for update	Section and title impacted (Current)
20-Sep-2021	Prior to DB lock	Creation of amendment (version 2) to MDCO SAP version v1.2 using Novartis template.	Amendment based on Novartis template.	All
24-Jan-2022	Prior to DB lock	Creation of amendment v03.	Removed “on-treatment” wording from diabetes analyses.	Section 2.7.4.2 and 2.7.4.3

## List of abbreviations

████	████████████████
ATC	Anatomical Therapeutic Chemical classification system
AE	Adverse Event
ALT	Alanine Aminotransferase
Apo-A1	Apolipoprotein A1
Apo-B	Apolipoprotein B
ASCVD	Atherosclerotic Cardiovascular Disease
AST	Aspartate Aminotransferase
BMI	Body Mass Index
CK	Creatine Kinase
CRF	Case Report Form
CRO	Clinical Research Organization
CRP	C-reactive Protein
CS	Clinically Significant
CSR	Clinical Study Report
████	████████████████
DBL	Database Lock
DMC	Data Monitoring Committee
DMS	Document Management System
EAIR	Exposure-Adjusted Incidence Rate
ECG	Electrocardiogram
eGFR	Estimated Glomerular Filtration Rate
EOS	End of Study
FAS	Full Analysis Set
HbA1c	Hemoglobin A1C
HDL-C	High-Density Lipoprotein Cholesterol
HLGT	High Level Group Term
HLT	High Level Term
IA	Interim Analyses
ITT	Intent-to-Treat
IXRS	Interactive Voice/Web Response System
LDL-C	Low-density Lipoprotein Cholesterol
LLN	Lower Limit of the Normal range
LMT	Lipid Modifying Therapy
Lp(a)	Lipoprotein(a)
████	██
MedDRA	Medical Dictionary for Regulatory Activities
MI	Myocardial Infarction
mITT	Modified Intent-to-Treat
PCS	Potentially Clinically Significant
PCSK9	Proprotein Convertase Subtilisin/Kexin Type 9

PK	Pharmacokinetics
PPS	Per-Protocol Set
█	█
RAP	Reporting & Analysis Process
SAE	Serious Adverse Event
SAP	Statistical Analysis Plan
SAS	Statistical Analysis System
SC	Subcutaneous
SD	Standard Deviation
SGOT	Serum Glutamic Oxaloacetic Transaminase
SGPT	Serum Glutamic Pyruvic Transaminase
SMQ	Standardized MedDRA queries
SOC	System Organ Class
PT	Preferred Term
TC	Total Cholesterol
TEAE	Treatment Emergent Adverse Event
TESAE	Treatment Emergent Serious Adverse Event
TFLs	Tables, Figures, Listings
█	█
ULN	Upper Limit of the Normal range
VLDL-C	Very Low-Density Lipoprotein Cholesterol
WHO	World Health Organization

## 1 Introduction

This document contains details of the planned statistical methods and analyses that will be used for the final clinical study report (CSR) of Phase II open label extension trial CKJX839A12201E1. The purpose of this study is to evaluate the efficacy, safety, and tolerability of long-term dosing of inclisiran in subjects with atherosclerotic cardiovascular disease (ASCVD) or ASCVD-risk equivalents and elevated low-density lipoprotein cholesterol (LDL-C) despite maximum tolerated dose of LDL-C lowering therapies. This statistical analysis plan (SAP) has been prepared based on clinical trial protocol CKJX839A12201E1 (MDCO-PCS-16-01) global amendment 5, content final dated 07-Oct-2020.

### 1.1 Study design

This study will be an open label, long term extension study with two arms. Group 1 (inclisiran only arm) will receive inclisiran only and Group 2 (switching arm) will receive an active comparator (evolocumab) for one year followed by inclisiran. The study will be conducted in subjects with ASCVD or ASCVD-risk equivalents (eg, diabetes and familial hypercholesterolemia) and elevated LDL-C despite maximum tolerated dose of LDL-C lowering therapies who have completed study MDCO-PCS-15-01 (ORION-1/CKJX839A12201), to evaluate the efficacy, safety, and tolerability of long-term dosing of inclisiran. All eligible and willing subjects who have completed the ORION-1 study to at least Day 210, and subjects whose LDL-C has returned to within 20% of the Baseline of ORION-1 value or who have reached Day 360 can be enrolled into the ORION-3 study. The study will be a multi-national, multi-center study (approximately 60 centers). Informed consent will be obtained from subjects before the initiation of any study-specific procedures.

Subjects completing study MDCO-PCS-15-01 and fulfilling all inclusion and exclusion criteria of this study will receive inclisiran or evolocumab, based on the treatment received in study MDCO-PCS-15-01. In countries where applicable, on signing consent and being entered into this study, the investigator will be informed by the Interactive Voice/Web Response System (IXRS) regarding the treatment allocation, and therefore, whether placebo or inclisiran was administered in study MDCO-PCS-15-01 (CKJX839A12201) and the subject will be informed accordingly. Those subjects who received inclisiran in MDCO-PCS-15-01 will receive inclisiran sodium throughout this study (Group 1; inclisiran only arm), and those subjects who received placebo in MDCO-PCS-15-01 (CKJX839A12201) will receive evolocumab as comparator for 1 year, and then transition to inclisiran for the remainder of the study (Group 2; switching arm). Until study drug is available, subjects will have monthly observation visits until study drug administration commences.

Day 1 of ORION-3 is the day when eligible subjects will receive the first subcutaneous (SC) administration of inclisiran or evolocumab.

#### **Group 1 (Inclisiran Only Arm):**

After first study drug administration of inclisiran, all subjects will be observed in the clinic for at least 4 hours post injection before being discharged.

The subsequent visit schedule is as follows:

- Dosing visits: Every 180 days until Day 720, an additional dose on Day 810, then back to every 180 day dosing until end of study (EOS). Therefore, dosing after Day 1 (ORION-3) will occur on Days 180, 360, 540, 720, 810\*, 990, 1170 and 1350.  
\*Day 810 dose added to assess the effect of giving 2 doses 90 days apart (at Days 720 and 810).
- Safety follow-up visits: Days 30, 90, 210, 270, 390, 450, 570, 630, 870, 1080, 1260, and EOS (Day 1440).
- The primary analysis time point is Day 210.

### **Group 2 (Switching Arm):**

Subjects receiving evolocumab will receive the first dose on Day 1 (ORION-3), administered by the investigator at the site, and will then self-administer evolocumab at home every 14 days until Day 336. Sites will then be assigned to have their evolocumab treated subjects placed into one of two transition groups.

- Transition 1 (staged): Day 336 will be the final dose of evolocumab therapy and the first dose of inclisiran will be administered at the Day 360 visit.
- Transition 2 (concurrent): Day 336 will be the final dose of evolocumab therapy at home. At the Day 360 visit subjects will receive an additional dose of evolocumab and their first dose of inclisiran, both administered by the investigator.

After first study drug administration of inclisiran on Day 360, all subjects in Group 2 (switching arm) will be observed in the clinic for at least 4 hours post injection before being discharged.

The subsequent visit schedule is as follows:

- Dosing visits: Day 450 (2nd dose), then every 180 days until end of study (Days 630, 810, 990, 1170 and 1350).
- Safety follow-up visits: Days 390, 510, 540, 720, 900, 1080, 1260, and EOS (Day 1440).

### **End of Study (EOS)**

EOS visit will occur at Day 1440, 90 days after the final administration of study drug (at Day 1350). However, if the study ends early or if the subject discontinues the study, the EOS visit should occur at least 30 days following the final administration of study drug.

Efficacy assessments will measure the effects of inclisiran on levels of LDL-C, lipids and lipoproteins including total cholesterol (TC), triglycerides, high-density lipoprotein cholesterol (HDL-C), non-HDL-C, very low-density lipoprotein cholesterol (VLDL-C), apolipoprotein A1 (Apo-A1), apolipoprotein B (Apo-B), lipoprotein(a) (Lp(a)), C-reactive protein (CRP), and proprotein convertase subtilisin/kexin type 9 (PCSK9).

At each visit, adverse events (AE), serious adverse events (SAE), concomitant medications, and safety laboratory assessments will be collected.

A Data Monitoring Committee (DMC) will review on a regular schedule the safety data. A recommendation may be taken to stop the study at any of these reviews.

Subjects enrolled into this extension study will receive study drug for approximately 4 years or

- until the investigator's recommendation of discontinuation,
- until the sponsor's recommendation of discontinuation,
- until the subject's decision to discontinue for any reason,
- until an administrative decision is made to end the study

[figure not shown]
If subjects, who have completed EOS visit (90 days after last dose administration), wish to continue treatment with inclisiran (and none of the above listed decisions or recommendations to discontinue the trial are in place) they will be given the opportunity to enroll into ORION-8 (open-label extension trial).

The protocol described the conduct of an interim analysis of lipids and PCSK9 upon completion of Day 210 for subjects in Group 1 (inclisiran only arm). Although there was a review of data upon completion of Day 210 for subjects in Group 1, no formal interim analysis report was generated. An interim analysis was conducted to evaluate Group 1 safety and tolerability data after all Group 1 subjects completed 24 months of treatment with inclisiran.

A schematic diagram of the study design is presented in [Figure 1-1](#).

**Figure 1-1 Study design**

## 1.2 Study objectives, endpoints and estimands

This study is designed to evaluate the efficacy, safety, and tolerability of inclisiran injection(s). The objectives and the corresponding endpoints are listed in [Table 1-1](#).

**Table 1-1 Objectives and related endpoints**

Objectives	Endpoints

Primary objective The primary objective of this study is: To evaluate
 
 
The effect of inclisiran treatment on LDL-C levels at Day 210 compared to Baseline of ORION-1 in Group 1 (inclisiran only arm).
 
	
Endpoint for primary objective
 
 
The percentage change from Baseline of ORION-1 in LDL-C at Day 210 in this study (Group 1; inclisiran only arm).
 

Secondary objectives The secondary objectives of this study are:
 
 
To evaluate the effect of inclisiran on the following (Group 1; inclisiran only arm): 
 
LDL-C levels over time
 
PCSK9 levels over time
 
Other lipids, lipoproteins, and apolipoproteins over time
 
 
 
	
Endpoints for secondary objectives (all for Group 1; inclisiran only arm)
 
 
Observed value, absolute change and percentage change from Baseline of ORION-1 in LDL-C over time in this study
 
Change and percentage change in LDL-C at Day 210 compared to Day 870 of ORION-3
 
Observed value, absolute change and percentage change from Baseline of ORION-1 in PCSK9 levels over time in this study
 
Observed value, absolute change and percentage change from Baseline of ORION-1 in other lipids, lipoproteins, and apolipoproteins, over time in this study
 

Objectives	Endpoints
[REDACTED]	[REDACTED]

## 2 Statistical methods

### 2.1 Data analysis general information

All analyses will be performed by Novartis or a designated clinical research organization (CRO). The most recent version of SAS available in the statistical programming environment of Novartis or the designated CRO will be used for the analysis.

All study-collected data will be summarized by treatment group using descriptive statistics, graphs, and/or raw data listings. Categorical variables will be summarized using counts and percentages. Percentages are based on the number of subjects in the analysis set for whom there are non-missing data, unless otherwise specified. Continuous variables, including changes from Baseline of ORION-1 or ORION-3, will be summarized using descriptive statistics (n (number of non-missing observations), mean, standard deviation (SD), median, first and third quartiles, minimum and maximum). The precise definitions of the baselines are given in [Table 2-1](#).

Absolute change and percent change from baseline will be calculated as follows:

- Absolute Change from baseline to Day X = Value at Day X – Baseline value.
- Percent Change from baseline to Day X = (Absolute Change/Baseline value)\*100%.

Analyses for the final CSR will be conducted after all participants complete the EOS visit or discontinued early. [REDACTED]

Information regarding DMC analysis will be provided in the DMC charter and a separate DMC SAP/TFL shells.

## 2.1.1 General definitions

### Study drugs

The study drugs in this trial are the following:

- Investigational drug: Inclisiran will be administered as a single SC injection of 300 mg inclisiran sodium (equivalent to 284 mg inclisiran)/1.5 mL
- Comparator drug: Evolocumab (REPATHA®) will be administered as a single SC injection at 140 mg.

### Date of first/last administration of study drug

Date of first/last administration of study drug is defined as the first/last date of administration of either inclisiran or evolocumab in ORION-3, unless otherwise specified.

### Gap period

The time between the end of ORION-1 and the beginning (date of informed consent) of ORION-3 is called the gap period.

### Study day

Study day will be defined as the number of days since the date of first administration of study drug. The date of first administration of study drug will be defined as Day 1 and the day before the first administration of study drug will be defined as Day -1.

Therefore, for a particular date, study day will be calculated as follows:

For dates on or after the date of first administration of study drug,

$$\text{Study day} = \text{Assessment date} - \text{Date of first administration of study drug} + 1;$$

For dates prior to the date of first administration of study drug,

$$\text{Study day} = \text{Assessment date} - \text{Date of first administration of study drug}.$$

### Baselines

Depending on the specific analysis, either baseline of ORION-1 or baseline of ORION-3 is considered. The precise definitions of the baselines for each analysis are summarized in [Table 2-1](#).

**Table 2-1 Summary of baselines**

Analysis category	Analysis	Baseline used	Explanation
Baseline Characteristics	Age*, weight, body mass index (BMI), country	Study entry of ORION-3	To provide a more accurate value of parameters that may change, baseline of ORION-3 is used.

	Estimated glomerular filtration rate (eGFR)	Last non-missing record prior to first study drug administration of ORION-3	To provide a more accurate value of parameters that may change, baseline of ORION-3 is used.
	Sex, race, ethnicity, height	Screening period of ORION-1	These values will not change or will not change significantly so baseline of ORION-1 is used.
	Medical history	Day 1 of ORION-1	Medical history is reported prior to the first treatment in ORION-1, after which any new medical conditions will be captured as AEs.
Prior and concomitant therapies	Concomitant Medications	Day 1 of ORION-3	Medications taken on or after Day 1 of ORION-3 will be considered as concomitant for ORION-3.**
Efficacy	Efficacy parameters in Group 1 (inclisiran only arm)	Baseline of ORION-1***	Due to residual efficacy from ORION-1, the true change from baseline should use baseline of ORION-1, i.e. prior to receiving any dose of inclisiran.
	Efficacy parameters in Group 2 (switching arm)	Baseline of ORION-3****	Placebo was given in ORION-1 and since treatment adjustments may have occurred during ORION-1 in lipid modifying therapies (LMT), baseline of ORION-3 will be used.
Safety	Adverse events	Day 1 of ORION-3	Previous AEs are collected in ORION-1, the gap period and the observation period so TEAEs in ORION-3 are collected from Day 1 (first dose) of ORION-3.
	Electrocardiograms (ECG)	Day 1 of ORION-3	To identify untoward change in ECG within ORION-3
	Safety laboratory parameters, vital signs	Baseline of ORION-3****	To identify untoward change in safety laboratory parameters and vital signs within ORION-3

\* Since age will not be re-collected in ORION-3, the age at ORION-3 baseline is inferred using the ORION-1 baseline:

- If the difference between consent date in ORION-3 and ORION-1 is greater than 365 days for a subject then 1 year will be added to the age at ORION-1 baseline;
- Otherwise, ORION-1 baseline age will be used.

\*\* Although all medications received 30 days prior to consent in ORION-1 through the EOS in ORION-3 will be reported, only medications taken on or after Day 1 of ORION-3 will be considered concomitant for ORION-3.

\*\*\* For PCSK9, lipids, lipoproteins and apolipoproteins, the last available record prior to first study drug administration in ORION-1 will be used as the baseline for Group 1.

\*\*\*\* The last available record in ORION-3 prior to first study drug administration will be used as the baseline for safety laboratory parameters, vital signs and Group 2 efficacy parameters, unless otherwise specified.

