1.2.2 Clinical Studies

One Phase I study has been conducted to date (Study ALN-PCSSC-001). This was a randomized, single-blind, placebo-controlled, single-dose escalation and multiple-dose study of inclisiran administered SC to subjects with elevated LDL-C. The study was conducted in two phases: a single ascending dose (SAD) phase and a multiple dose (MD) phase. During the SAD phase, 24 subjects were assigned to either receive placebo or one of five doses of inclisiran ranging from 25 mg to 800 mg. Those who received doses of at least 100 mg saw their LDL-C drop at least 40%; at the 500 mg dose, LDL-C levels dropped as much as 78%. At 140 days after the treatment was given, subjects still had an average LDL-C reduction of about 40%.

In the MD phase, 45 subjects received multiple doses of either inclisiran (125mg weekly x4, 250 mg biweekly x2, 300 mg and 500 mg twice given 1 month apart) or placebo. These subjects had maximal LDL-C reductions of 80% and average LDL-C reductions of 50% to 60%. To date, the drug appears to be generally safe and well tolerated. One subject on statin comedication had elevated liver enzymes with alanine aminotransferase (ALT) >4x the upper limit of normal (ULN), which resolved on stopping the statin.

One Phase II dose finding study CKJX839A12201 (MDCO-PCS-15-01; ORION-1) was conducted and is complete. This study was a placebo-controlled, double-blind, randomized trial to compare the effect of inclisiran administered SC as either a single dose (200 mg, 300 mg, or 500 mg) on Day 1 or as two doses (100 mg, 200 mg, or 300 mg) on Day 1 and Day 90 in subjects with high cardiovascular risk and elevated LDL-C. A total of 501 subjects were randomized (placebo=127 and inclisiran=374) and 497 received at least one dose of study drug (placebo=127 and inclisiran=370). After administration of dosing, all subjects were followed until Day 210. Subjects whose LDL-C values had not returned to within 20% of the change from their baseline value were followed up to Day 360. Regular reviews of safety were performed by an independent Data Monitoring Committee and no safety concerns were reported and no changes to the protocol were requested during conduct of the study.

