10.1 Sample Size

This is an extension of the MDCO-PCS-15-01 (CKJX839A12201) (ORION-1) study. All eligible and willing subjects who have completed the ORION-1 study to at least Day 210 and whose LDL-C has returned to within 20% of the Baseline of ORION-1 value or who have reached Day 360 can be enrolled into the ORION-3 study. Subjects withdrawn from the ORION-1 study at any time are not eligible for the ORION-3 study.

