### **2.3.2 Demographics and other baseline characteristics**

Subject demographics and background characteristics including age, sex, weight, height, BMI, race, ethnicity, country (country of participation), baseline eGFR and re-evaluation of child-bearing potential will be summarized using the ITT population. The following categorizations of quantitative variables will be performed:

- Age into  $\geq 18 - < 65$  and  $\geq 65$
- Age into  $\geq 18 - < 50$ ,  $\geq 50 - < 65$ ,  $\geq 65 - < 75$ ,  $\geq 75$
- Baseline eGFR into  $\geq 15 - < 30$ ,  $\geq 30 - < 60$ ,  $\geq 60 - < 90$ ,  $\geq 90$

Age collected in ORION-1 will be used but if the difference between consent date in ORION-3 and ORION-1 is greater than 365 days for a subject then 1 year will be added to the age for this subject.

Medical history (targeted and other medical history) will be summarized using the safety population. Other medical history will be coded into Medical Dictionary for Regulatory

Activities (MedDRA) terminology using the most recent MedDRA version before database lock (DBL), and will be summarized by primary system organ class and preferred term.

Summaries will be presented overall and by group (Group 1 and Group 2). Select tables for Group 2 will be broken down by transition group (Transition 1 (staged) and Transition 2 (concurrent)).

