## 3 Sample size calculation

This is an extension of the Phase II ORION-1 (CKJX839A12201; MDCO-PCS-15-01) study. All eligible and willing subjects who have completed the ORION-1 study to at least Day 210 and whose LDL-C level returned to within 20% of the Baseline of ORION-1 value or who have reached Day 360 can be enrolled into this study. Subjects withdrawn from the ORION-1 study at any time will not be eligible for this study.

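### Age at ORION-3 entry rises by a year only after a consent gap above 365 days, so ages left unchanged are probably one year too low, in the descriptive baseline table only

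*SAP*

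**What the plan says.** SAP Table 2-1 places age, with weight, BMI and country, at ORION-3 study entry and gives the reason: "To provide a more accurate value of parameters that may change, baseline of ORION-3 is used". A footnote explains how age is obtained: "Since age will not be re-collected in ORION-3, the age at ORION-3 baseline is inferred using the ORION-1 baseline". The rule then has two branches. The first is "If the difference between consent date in ORION-3 and ORION-1 is greater than 365 days for a subject then 1 year will be added". The second is "Otherwise, ORION-1 baseline age will be used".

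SAP 2.3.2 repeats the rule for the demographics table ("Age collected in ORION-1 will be used but if the difference between consent date in ORION-3 and ORION-1 is greater than 365 days") and sorts age into two sets of categories, one cut at 65 and one cut at 50, 65 and 75. The summaries are shown overall and by group.

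The time between the two consents has a lower limit. Protocol 10.1 admits "All eligible and willing subjects who have completed the ORION-1 study to at least Day 210", subject to a further LDL-C or Day 360 condition, and SAP section 3 says the same. Protocol 1.2.2 says of ORION-1: "After administration of dosing, all subjects were followed until Day 210". Protocol 6.2 places ORION-3 consent after completion of ORION-1, and Protocol 10.1 bars anyone who withdrew from ORION-1.

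**The concern.** Age in completed years changes on a birthday, not after a full year has passed. Someone who consents again eight or nine months later has more often than not had a birthday in between. The rule takes an age already rounded down and adds elapsed time that is also rounded down to whole years, so its errors fall on the low side and do not cancel.

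The Day 210 requirement means that no eligible subject has a gap short enough for an unchanged age to be the better guess. The rule therefore works against the accuracy that Table 2-1 gives as its reason for using ORION-3 entry. What is at stake is the mean age and the counts in the age categories of the baseline table. Those summaries are split by group, so groups that left ORION-1 at different times could be affected to different degrees.

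**Working it through.** The plan states no error rate for age, so there is no figure of its own to reproduce.

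**Inputs from the documents**
- Threshold: one year is added if the gap exceeds 365 days, and nothing otherwise (SAP Table 2-1 and 2.3.2).
- Shortest gap: Day 210 is 209 days after Day 1 of ORION-1. ORION-1 screening time and any gap period (SAP 2.1.1) can only lengthen it.

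**Assumptions not in the documents**
- ORION-1 age was recorded in completed years.
- Birthdays are spread evenly over the year.

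**Step 1: error for subjects left unchanged.** An unchanged age is wrong when a birthday falls inside the gap of d days, so for d up to 365, P(one year too low) = d / 365.25. Adding one year instead is wrong when no birthday falls inside the gap, so P(one year too high) = 1 − d / 365.25.

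| Gap (days) | Unchanged: too low | One year added: too high |
|---|---|---|
| 210 | 210/365.25 = 57% | 43% |
| 270 | 270/365.25 = 74% | 26% |
| 300 | 300/365.25 = 82% | 18% |
| 330 | 330/365.25 = 90% | 10% |
| 360 | 360/365.25 = 99% | 1% |

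Break-even is 365.25 / 2 = 182.6 days, about 26 days below the 209-day minimum. A calendar-date simulation with 100,000 subjects per gap agrees: 57.5% at 210 days, 74.0% at 270 and 98.6% at 360. If gaps were spread evenly over 210 to 365 days, the average error for an unchanged age would be 78.7%.

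**Step 2: sensitivity.** The ORION-1 visit window is not given. A Day 210 visit 7 days early (203 days) gives 55.6%, and one 14 days early (196 days) gives 53.7%. With birth seasonality of 10% placed as unfavourably as possible, a 209-day gap still gives 54.2%; with 20% it gives 51.1%.

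**Step 3: effect on the reported mean.** Let f be the share of subjects with a gap of 365 days or less, and m their average understatement in years (0.57 at 210 days, 0.99 at 360). Through these subjects the mean is low by f × m. The documents do not give f, so a range is assumed:
- f = 10%: 0.10 × 0.57 = 0.06 to 0.10 × 0.99 = 0.10 years.
- f = 60%: 0.60 × 0.57 = 0.34 to 0.60 × 0.99 = 0.59 years.

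Only subjects within one year below a cut-point can change category, and the documents do not give that number either.

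**The case against.** The strongest reply concerns reach. The percentages apply only to subjects left unchanged, and those may be a minority, at least of Group 1. Protocol 1.2.2 says that subjects whose LDL-C had not returned towards baseline were followed to Day 360, and that the reduction lasted that long. Day 360 is 359 days after Day 1, so once screening plus any gap period exceeds about a week, such a subject passes 365 days and receives the added year. This stands. A reader might infer from the 57% to 99% figures that the mean age in the whole table is low by 0.57 to 0.99 years. The documents do not support that, because the share of subjects concerned is not given.

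Second, the result depends on how ORION-1 age was derived. If it was consent year minus birth year, it already runs one year high for anyone whose birthday had not yet come, and leaving it alone would be right more often than the table shows. The documents do not settle this, so a reader should not conclude unconditionally that every unchanged age is more likely wrong than right.

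Third, the rule is an openly stated convention, applied the same way in both places. This also stands: it is a weak imputation rule, and no figure in the SAP is miscalculated.

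Fourth, age has no inferential role. The primary analysis is a one-sample t-test and confidence interval without covariates (SAP 2.5.1), the secondary analyses are summaries with confidence intervals (2.6.1), and subgroup analyses are ruled out (2.2.1). This is correct and limits the importance of the point.

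A spurious age difference between groups is possible if placebo subjects left ORION-1 sooner. Actual gap lengths are not in the documents, so this remains a possibility only.

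**Conclusion.** The point holds as a minor defect in a derivation rule. Given completed years and evenly spread birthdays, an age left unchanged is one year too low with probability 57% at a 210-day gap and 99% at 360 days. Adding a year would be wrong less often at every eligible gap up to 365 days. The conclusion survives moderately early ORION-1 visits and strong birth seasonality; it would reverse only for gaps under about 183 days, which the Day 210 requirement excludes unless a visit fell more than about 26 days early.

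The effect on the overall or group mean is not known. The range of 0.06 to 0.59 years rests on an assumed share of 10% to 60%. It would be tempting to read this as a threat to the trial's results, but it touches only the descriptive baseline table.

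**What to change.** In SAP Table 2-1 and 2.3.2, derive age from full date of birth and ORION-3 consent date if the date of birth is held. Year of birth alone does not give completed age. Otherwise add the consent gap rounded to the nearest whole year, which means one year from 183 days. Derive the age categories from the resulting value.

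An acceptable alternative is to drop the adjustment and label the variable as age at ORION-1 baseline, which is then accurate as described.

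The cost is one derivation and a line of text in two places, with no new data. The downside of the rounded fallback is that it still misstates some individual ages by one year, now upward: 43% at a 210-day gap, falling to 1% at 360 days. Reporting the number of subjects with a gap of 365 days or less would show how much the choice matters.
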